### *(iii.2) Procedure of Part II study*

**Part II** study includes longitudinal quantitative study (i.e., prospective cohort study) from the timeline of 1.5th – 4.5th year involving an overall 1,495 workers recruited at the baseline survey from non-office, mobile and office work settings. At the baseline survey, 1,495 workers from 3 studied work settings will be invited to respond to a standardized questionnaire on exposure,

prevention and attitude towards outbreaks, and willingness to be tested for COVID-19 and receiving vaccination. Results obtained from the baseline and follow-up surveys will be compared to understand the changes of attitudes, awareness, willingness to vaccination and virus test, and workplace risk profile of workers towards prevention and control of COVID-19.

### **Cohort enumeration at baseline and follow-up:**

A two-stage sampling method will be employed to recruit 1,495 eligible cohort members at the baseline survey for the Part II longitudinal quantitative study (i.e., prospective cohort study) in the timeline of 1.5th-2.5th year. In stage one, we plan to invite local workers unions with non-office, mobile and office work settings through our networks and connections, such as the Federation of Hong Kong and Kowloon Labour Unions (FLU). There are more than 150 local worker unions under the network of FLU, covering a variety of types of worker unions including restaurants, transportation, construction, telephone and communication, etc. In stage two, we will then recruit about 1,495 workers from the worker unions who agree to participate in the Part II study of our project. However, the baseline recruitment of Part II study subjects will be stopped if the required sample size of workers is reached.

All eligible subjects recruited at the baseline will be invited to participate in the follow-up survey in the timeline of 3.5th- 4.5th year to compare the changes of attitude to vaccination and virus testing as well as risk profile toward infection control in the workplace through various means (e.g., telephone, email, worker unions). Any loss-to-follow-up will be recorded.

Participants who complete the whole questionnaire of the baseline or follow-up quantitative survey will receive 200HKD fast food restaurant / supermarket coupon, and if the participant completes both the baseline and follow-up quantitative questionnaire survey, she/he will receive a total of \$400 fast food restaurant / supermarket coupon as a token of appreciation.

### **Questionnaire development:**

A standardized questionnaire is designed to capture each participant's information on knowledge, attitude and awareness towards SARS-CoV-2, exposure prevention behaviour, and willingness to vaccination and virus testing, with key items on –

- General introduction
- Employment status, industry background and occupation, job nature and tasks, demographics
- Worker's exposure and prevention profile towards risks of outbreaks, including knowledge of engineering and administrative control measures (e.g., proper utility of personal protective equipment, social distancing), safety culture, types of occupational hazards/hazardous process
- Attitude and willingness to vaccination and SARS-CoV-2 testing, and barriers
- Previous work and related exposure behaviour and behaviour intention towards prevention of infectious diseases in the workplace

### ***(iii.3) Procedure of Part III study***

**Part III** study includes longitudinal qualitative studies in the timeline of 1.5th – 4.5th year involving an overall 26 management and frontline workers recruited at the baseline survey from non-office, mobile and office work settings. Part III study aims at understanding the level of administrative controls in workplace, awareness of virus testing and vaccination and barriers of the selected workplaces over time. At the baseline of longitudinal qualitative study, a total of 26 management staff and frontline workers (in a ratio of 1:2, and after considering a potential loss-to-follow-up rate of about 40%) will be simultaneously invited to participate in in-depth interviews using qualitative approach to understand the measures of administrative controls of their workplaces using a standardized checklist questionnaire developed according to scientific literature and documentation review from international organizations, e.g., OSHA, NIOSH, ILO. The developed checklist questionnaire will be used as international benchmark to evaluate level of measures of control achieved by the respective work settings. In addition, their barriers and challenges in getting COVID-19 vaccination and testing will also be investigated. The value of qualitative inquiries is to suffix an in-depth understanding of the reasons of the views they hold, and the vaccine decision making that are more complex in real life. It will also be useful to capture factors attributable to vaccine rejection, hesitancy or acceptance. The insights generated from the qualitative study (e.g., detailed barriers and attitudes) will inform questionnaire design in the longitudinal quantitative study and also help to explain the results from other parts of this proposed project.

**Recruitment of longitudinal qualitative study and follow-up:** At the baseline of longitudinal qualitative study, we target a total quota of 26 (18\*1.4) management staff and frontline workers (in ratio of 1:2) selected from the studied work settings using the same eligible criteria as the Part II quantitative surveys, assuming a potential loss-to-follow-up rate of about 40%. In general, two workplaces from each of the selected work setting will be invited. The rationale of the choice of workplaces is based on their relevance to selected settings, *for example*:

- Group (1) Non-office: waiters/waitresses from catering companies, construction workers from construction companies
- Group (2) Mobile: taxi drivers, delivery men, social care workers who pay visit to individuals and families to provide social care, and international transport workers, such as air crew members, seafarers, and cross-border drivers)
- Group (3) Office: office assistants, clerks, and officers

Subjects in Group (1), (2) and (3) will be recruited through Workers' Union that have access to members who are our targeted work settings and occupations. Recruitment will be completed when data saturation is reached.

All eligible subjects recruited at the baseline (1.5th-2.5th) of longitudinal qualitative study will be invited to participate in the follow-up survey in the timeline of 3.5th- 4.5th year, in parallel

with the Part II longitudinal quantitative study and Part IV longitudinal workplace hygiene study. Any loss-to-follow-up will be recorded.

*Interview guide and data collection for longitudinal qualitative study:* In addition to a short questionnaire enquiring the personal profile of participants, a semi-structured 60-min interview guide asking open-ended questions will be developed based on literature reviews and expert advice from our multidisciplinary research team.

A trained Research Assistant with good knowledge of the subject area and qualitative interview skills will conduct the interview with written consent obtained in prior. Each will last around 45-60 minutes, be audio-taped and held at the meeting room of our research centre or Workers' Union, with privacy maintained. Each participant will receive HK\$200 fast food restaurant / supermarket coupon; and if he/she complete either the baseline or follow-up qualitative interview, and if the participant completes both the baseline and follow-up qualitative interview, then she/he will receive a total of \$400 fast food restaurant / supermarket coupon as a token of appreciation.

### ***(iii.4) Procedure of Part IV study***

**Part IV** includes a longitudinal workplace hygiene study in parallel with the **Part II and Part III** study during the timeline 1.5th – 4.5th, aiming at conducting repeated workplace hygiene study and assessment in selected work settings to systematically identify workplace hazards and/or hazardous process related to infection, and evaluating the existing control measures according to occupational health hazard evaluation.

The longitudinally repeated workplace hygiene study will focus on different indoor microenvironments of overall 18 workplaces from 3 selected work settings in Hong Kong industries over 5-year timeline, i.e., 6 workplaces from non-office, 6 workplaces from mobile and 6 workplaces from office work setting. Direct contact is one of the important transmission pathways for SARS-CoV-2, but how to use ventilation to improve aerosol/droplets transmission is our major task. Data collection and timeline of this longitudinal workplace hygiene study will follow the workflow chart of **Figure 1**. We will measure the geometry and thermo-fluid boundary conditions in indoor microenvironments. A 3D digital model will be built with several heated manikins to simulate different scenarios with different numbers of people/workers in indoor. The airflow, turbulence, and temperature distributions will be calculated using the RNG k- $\epsilon$  turbulence model. This model has the best overall performance among all Reynolds-averaged Navier-Stokes (RANS) models for enclosed environments. The transient exhaled pathogen transport will be calculated using the Lagrangian tracking method. The Lagrangian method calculates the trajectories of individual pathogen-containing particles on the basis of Newton's law. The discrete random walk (DRW) model will be used to calculate the turbulence dispersion.

With the calculated exhaled pathogen-containing particle (aerosol/droplets) distribution, we can predict the “hotspots” (aerosol/droplets) with relatively high pathogen concentrations and understand how the exhaled pathogen-containing particles (aerosol/droplets) transport from the person to person. The information about these hotspots will be provided to the property management team for control strategies (e.g. ventilation control or disinfection “hotspots”). In order to reduce the person-to-person transmission in confined area, this project will propose several partitioning strategies for blocking aerosol/droplets transmission routes. The proposed partitioning strategies will also be assessed using the CFD model. The calculated results will reveal whether the intervention strategies are effective or not.

Findings from the longitudinal hygiene study will provide objective evidence to validate the self-report of workers from same work settings and inform management for engineering control and workstation modification.

### ***(iii.5) SARS-CoV-2 antibody rapid test***

All participants of the RCT who do not finish COVID-19 vaccination will be invited to take the SARS-CoV-2 antibody rapid test four times points during the study to observe their attitudes toward antibody tests and their actual updates of the testing and compare the differences between the intervention and control group, i.e., at baseline, 3rd month, 6th month and 9th month of the RCT. We are also interested in inviting and welcoming those already with complete vaccination to participate in the SARS-CoV-2 antibody rapid test to understand their attitudes towards antibody testing and actual uptakes, and same primary outcomes between the intervention and control arms will be compared. The self-sampling test kit will detect the IgG/IgM antibody of SARS-CoV-2 from whole blood with above 90% sensitivity and specificity, which is recommended by US FDA.

### **(iv) Data processing & analysis**

For quantitative results, descriptive analysis and Chi-square will be used for baseline data to analyse the difference in exposure and prevention, willingness to vaccination/testing and actual uptake of tests between comparison groups (e.g., work settings). Paired t-test and covariance analysis will be performed to compare the longitudinal changes of scores of each exposure prevention behaviour factors, attitude and willingness to vaccination and virus testing over time. Structural equation modelling and multivariate regression logistic modelling will be used to analyze the structural relationship between measured variables and latent constructs, as well as examine the association of exposure profile with willingness to vaccination/testing or uptake testing. Effectiveness of intervention will be examined by multivariable linear (for continuous nature of outcome) or Cox proportional hazard models (for binary outcome). Loss-to-follow-up will be reported and intention-to-treat analysis will be used for addressing the loss-to-follow-

up issue of the RCT. All statistical analyses for longitudinal quantitative and RCT data will be conducted by SPSS Version 26 and/or SAS 9.4 (SAS Institute Inc., North Carolina). P-value of less than 0.05 is considered statistically significant.

For qualitative analysis, the tape-recorded individual interviews will be transcribed verbatim and thematically analysed using Grounded Theory approach. Data will be horizontally compared between participants, and longitudinally analysed, tracking and explaining attitudinal and behavioral changes of individuals across time. The qualitative data will be delineated to a typology of reasons for (1) accepting, delaying or refusal of COVID-19 vaccine, and (2) factors contributing to uptake of COVID-19 testing in the workplace, generated through thematic analysis.

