### **(ii) Subjects to be included**

**Study subjects:** In the Part I randomized controlled trial (RCT), 294 eligible workers from 3 non-healthcare work settings will be recruited, and randomized into intervention group (147 subjects) and control group (147 subjects). To be eligible to the Part I RCT, all participants are required to be aged 18 or above, who can read Chinese and currently being employed in three non-healthcare work settings from non-office, mobile, and office work environment in Hong Kong. We attempt to follow-up all participants of the RCT for 9 months to observe the effectiveness of the intervention on improving the primary outcomes, i.e., attitude to vaccination and SARS-CoV-2 testing.

In Part II longitudinal quantitative study, we plan to recruit a total of 1,495 workers who are aged 18 or above and currently working in non-office, mobile, or office work setting in Hong Kong. All eligible study subjects in Part II longitudinal/ prospective cohort study will be recruited in the timeline of 1.5th -3.5th year of the project and followed up for 2 years to observe the changes of attitude to vaccination and virus testing as well as risk profiles of workers towards outbreaks over time.

Figure 1. Workflow chart of hazard identification of outbreaks and control measures in work settings

\* After considering a lost-to-follow-up rate of about 40%

In the Part III longitudinal qualitative study, we plan to recruit an overall 26 management staff and frontline workers (in a ratio of 1:2) with same inclusion/exclusion criteria as the Part I & II study, i.e., aged 18 or above and currently being employed in three non-healthcare work settings from non-office, mobile, and office work environment in Hong Kong.

All above planned number of participants to be enrolled in the baseline of the Part I, II and III study have already considered a potential loss-to-follow-up rate of about 40%.

**Settings:** The 3 work settings are categorized by types as below according to their job nature and working environment:

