We estimated sample size for the Part II – Longitudinal/prospective cohort study (quantitative survey) according to the formula for cohort studies. As there is no relevant publication for a reference, a conservative estimation is used to calculate the sample size for Part II study. For the estimation of the maximum sample size of longitudinally quantitative survey for the Part II study, the presumed population proportion is set as 0.5, which means that half of the workers have positive attitude to vaccination or willingness of SARS-Cov-2 virus testing in the selected work settings. It is estimated that a minimum of 1,068 workers is required for the longitudinal/prospective cohort study to accept an absolute sample error of 3.0% at 95% confidence level. Currently, there is not enough guideline for choosing an appropriate absolute error, and an absolute error of 5% is generally recommended in many studies. So, an absolute error of 3.0% employed in the project is more conservative than many other studies for sample size estimation. Although the required sample size is getting larger with the increase of population size, it will not change much when the population size is larger than 20,000. According to the latest statistics of the Census and Statistics Department of Hong Kong, the employed persons during 12/2020 - 2/2021 in Hong Kong are about 3.6 million, and therefore, it is appropriate to adopt this method of sample size calculation for a population-based cohort study in Hong Kong working settings. Assuming a potential loss-to-follow-up rate of about 40%, 1,495 workers are suggested to be recruited in the baseline survey for the Part II study.

While there is no established requirement for sample size estimation for the Part III and IV study which only involve qualitative approach and workplace hygiene measurement, it usually desires a reasonable sample size with representative sample. We plan to recruit 26 ( $18*1.4$ ) eligible subjects at the baseline from 3 defined work settings to participate in the Part III qualitative study and 6 representative workplaces for the Part IV study that are regarded as reasonable. We set the sample size according to number of participants/workplaces estimated to reach data saturation.

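### Part II change over two years would be estimated from returners only, with no stated method for the 40% loss the plan assumes, so the estimate can be biased if return and change both depend on baseline attitude

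*Combined protocol and SAP*

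**What the plan says.** The purpose of Part II is longitudinal. Section (ii) says that its workers will be "followed up for 2 years to observe the changes of attitude to vaccination and virus testing". There are two measurements: under the cohort enumeration heading, "All eligible subjects recruited at the baseline will be invited to participate in the follow-up survey", and no further wave is described.

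The sample size text in section (ii) plans for substantial loss: "Assuming a potential loss-to-follow-up rate of about 40%, 1,495 workers are suggested" for the baseline survey.

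Section (iv) gives the method for change: "Paired t-test and covariance analysis will be performed to compare the longitudinal changes of scores". The scores it goes on to list (prevention behaviour, attitude, and willingness to be vaccinated and tested) are the domains of the Part II questionnaire.

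On loss, section (iv) says "Loss-to-follow-up will be reported and intention-to-treat analysis will be used for addressing the loss-to-follow" and the sentence ends, over the page break, with "up issue of the RCT". For Part II, the cohort enumeration text says only: "Any loss-to-follow-up will be recorded". Nowhere do the documents give, for Part II, a weighting or imputation method, a likelihood-based repeated-measures model, a comparison of returners with non-returners, or a sensitivity analysis for loss.

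**The concern.** A paired t-test can use only workers who answered both surveys. Covariance analysis as written has the same limit, because it needs a follow-up score as its outcome. At the assumed loss, about 598 of the 1,495 baseline records contribute nothing to the estimate of change.

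That is harmless if returners change, on average, as the whole cohort does. It can fail when two things hold together: workers with one kind of baseline attitude are more likely to return, and the amount of change differs by baseline attitude. In a study about attitudes to vaccination and testing, neither should be ruled out without a check. What is at stake is the direction and size of the change that Part II sets out to observe. The baseline questionnaire already collects the variables needed to examine and adjust for this, but the stated test does not use them for workers who do not return.

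**Working it through.** **The plan's own numbers.** From the sample size text: proportion 0.5, absolute error 3.0%, 95% confidence, about 40% loss.

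- Minimum sample: 1.96² × 0.5 × 0.5 / 0.03² = 1,067.07, rounded up to 1,068. This matches the plan.
- Baseline recruitment: 1,068 × 1.4 = 1,495.2. This matches the plan's 1,495. (Whether 1.4 is the right inflation is a separate question.)
- Workers with both surveys at 40% loss: 1,495 × 0.6 = 897. Workers without: 1,495 − 897 = 598.

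**Illustration for a binary item.** The 50% positive at baseline and the 60% overall retention come from the plan. Two inputs are assumptions, because the documents give no figure: 80% of baseline-positive workers and 40% of baseline-negative workers are positive at follow-up; and retention is split by baseline attitude as shown in the table.

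- Full cohort at follow-up: 0.5 × 0.8 + 0.5 × 0.4 = 0.60, so the true change is +10.0 points.
- Share of returners positive at baseline: p = 0.5·r₊ / (0.5·r₊ + 0.5·r₋), where r₊ and r₋ are the retention rates of positive and negative workers.
- Returners at follow-up: 0.8p + 0.4(1 − p) = 0.4 + 0.4p.
- Paired change: (0.4 + 0.4p) − p = 0.4 − 0.6p.

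| Retention, positive / negative | Returners positive at baseline | Returners positive at follow-up | Paired change (points) | Bias (points) |
|---|---|---|---|---|
| 60% / 60% | 50.0% | 60.0% | +10.0 | 0 |
| 65% / 55% | 54.2% | 61.7% | +7.5 | −2.5 |
| 70% / 50% | 58.3% | 63.3% | +5.0 | −5.0 |
| 75% / 45% | 62.5% | 65.0% | +2.5 | −7.5 |
| 50% / 70% | 41.7% | 56.7% | +15.0 | +5.0 |

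Weighting removes the bias in this setting. At 70%/50%, the returners are 747.5 × 0.7 = 523.25 positive and 747.5 × 0.5 = 373.75 negative workers. Weights of 1/0.7 and 1/0.5 restore 747.5 of each, and the weighted change is +10.0.

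**The same check for a continuous score.** The quoted sentence is about scores, so the binary case is not enough. Take a standardised baseline score, a follow-up score with slope b on baseline, no true mean change, and 60% retention that depends on baseline through a probit model with correlation rho. The values of b and rho are assumptions. The paired bias is (b − 1) × rho × φ(z₀.₆)/0.6 = (b − 1) × rho × 0.644. Type I error is from 2,000 simulated cohorts of 1,495.

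| rho | b | Bias of paired change (SD) | Type I error of paired test |
|---|---|---|---|
| 0 | 0.5 | 0 | about 5% |
| 0.3 | 1.0 | 0 | about 5% |
| 0.1 | 0.5 | −0.03 | 16% |
| 0.2 | 0.5 | −0.06 | 48% |
| 0.3 | 0.8 | −0.04 | 43% |
| 0.3 | 0.5 | −0.10 | 82% |

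The first two rows show that both conditions are needed. In all six scenarios, regressing follow-up on baseline and standardising to all 1,495 baseline members gave a bias of 0.00 SD and a type I error of 4% to 6%.

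**Where the remedy stops working.** In one further simulation (rho = 0.3, b = 0.5) return also depended on the unseen follow-up score. The full-record analysis was then biased by +0.12 SD, against +0.02 SD for the paired test.

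**The case against.** The strongest reply is that the bias is conditional. The documents do not say that return is related to attitude; 40% is a planning allowance; and even attitude-related return leaves a paired mean change unbiased if change does not depend on baseline. This stands, and it rules out saying that the result will be biased. It does not make the conditions remote. On a binary item, positive workers can only stay or fall and negative workers can only stay or rise, so apart from an exact balance of the two flows' signs, which no switching alone can produce, change depends on baseline. On a score with stable variance, the slope is below 1 unless answers are perfectly stable over two years.

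Second, the sentence also names covariance analysis. Baseline adjustment can remove baseline-dependent loss bias from contrasts between groups such as work settings. It does not recover the mean change of the whole cohort unless it is standardised to all baseline members, and the plan does not say that it will be.

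Third, the sentence does not name Part II. Reading it that way is reasonable, since the RCT's effectiveness analysis has its own models.

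Fourth, the plan offers coupons for each completed survey and several routes of contact. These may improve retention, but they are not an analysis method.

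A reader might also infer a stronger point from section (iii.2): "Results obtained from the baseline and follow-up surveys will be compared to understand the changes of attitudes". Taken as all 1,495 baseline workers against about 897 returners, it would show a false rise of 8.3 points (58.3% against 50%) at 70%/50% retention even if nobody changed. The documents do not support that reading. The sentence is descriptive, and section (iv) names a paired test, which cannot make that comparison.

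**Conclusion.** The concern holds as a conditional one. For Part II the plan names completer-only methods, assumes about 40% loss, and states no way of handling that loss. The estimate of change can be biased if return and change both depend on baseline attitude; if either condition fails, the paired mean change is unbiased in the settings examined.

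Under the assumed 80%/40% follow-up proportions, the bias on a true +10.0-point change runs from 0 with equal retention to −7.5 points at 75%/45%, and reverses sign if negative workers return more. For a score it runs from 0 to about 0.10 SD over the range tabulated. As a yardstick only, the plan accepts an absolute error of 3.0 points for a single proportion; gaps of 70%/50% or more exceed it in this illustration.

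Two stronger inferences are not supported. One is that the cohort's result is biased as planned: no document shows attitude-related loss. The other is that this undermines the main result of Part II: the plan declares no primary outcome for Part II and sizes it on the precision of one proportion. The point does not concern the RCT.

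**What to change.** In section (iv), state a separate analysis of change for Part II that uses every baseline record. Either of these would do:

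- a likelihood-based two-wave mixed model with unstructured covariance, including baseline predictors of return; or
- returners weighted by the inverse of their probability of return, modelled on baseline attitude, work setting, occupation and demographics, all of which are on the questionnaire.

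If GEE is used for binary items, it should be inverse-probability weighted. Unweighted GEE with independence working correlation sets the full baseline (50%) against returners (63.3%) in the 70%/50% example, giving about +13 points against a true +10.

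Add a baseline table of returners against non-returners. Keep the paired completer test as a sensitivity analysis. Add a missing-not-at-random sensitivity analysis, because both options assume that loss depends only on observed data.

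No new data are needed. The cost is revised wording, a little more analysis work and slightly wider intervals.
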